### 3.4 Sample Size Consideration

In Part 1, Part 2, and Part 3, up to 65 evaluable patients will be enrolled. In Part 1, Dose Escalation, a total of two pre-defined dose levels will be studied. A conventional “3+3” design will be used during Part 1 for dose assessment and escalation. The first cohort of 3 patients will be enrolled at the lowest dose level. If 0/3 patients experience DLT, the next cohort will be enrolled into the next higher dose. If 1/3 patients experience DLT, the current dose level will be expanded to a total of 6 patients. If 1/6 patients experience DLT, dose escalation may occur. If 2 or more patients in dose cohort experience DLT at any time, the MTD has been exceeded. The MTD or maximum safe dose (if at the highest dose level) is defined as the highest dose in which less than one third of patients in the cohort experienced a DLT.

Once the MTD or maximum safe dose examined in the study has been determined, Part 2 will begin. In the optional Large Tumor group, up to 4 patients will be treated and safety will be examined.

In Part 2, Patient Expansion, up to 24 patients (12 per treatment group) will be randomly assigned to receive treatment with either G100 alone or the sequential administration of G100 and pembrolizumab. The dose of G100 will be the MTD / maximum safe dose determined in Part 1. This portion of the study will provide additional safety, immunogenicity and early efficacy data of G100 at the MTD / maximum safe dose and provide initial data on the sequential administration of G100 and pembrolizumab. This analysis is designed to be exploratory but will provide important data to guide further development. While the sample size is not based on formal power calculations, it is expected to provide adequate preliminary data to inform subsequent trials and to reject an indication should no clinical benefit occur. For example, if the true ORR is 20%, we will conclude futility with a 6.9% error rate if 0 response is observed in 12 patients. In that case, the Sponsor would terminate that study arm for development.

In Part 3, G100 Expansion of 20 µg Dose Group, up to 25 patients will be enrolled and treated with intratumoral G100 at 20 µg/dose following radiation therapy. The purpose of this group would be to explore the safety and potential clinical responses at the higher dose level. The number of patients was chosen to provide a similar cohort treated with G100 alone in Parts 1 and 2 for descriptive comparison.

In Part 4, G100 Plus Pembrolizumab, at least 22 evaluable patients will be enrolled and treated as part of a Dose Escalation group or a Patient Expansion group with intratumoral G100 in combination with pembrolizumab. The purpose of this treatment regimen will be to explore the safety and preliminary clinical efficacy and biomarker changes of patients treated with G100 at a dose of 20 µg/lesion injected in single or multiple lesions. The administered dose of G100 will depend on the number of potentially injectable lesions and whether the MTD has been established during Dose Escalation. One or more lesions will be targeted for injection and each lesion would receive 20µg of G100 intratumorally (or 10 µg G100 if 20 µg/lesion in a single lesion is not tolerated) as long as the total number of treated tumor lesions and total systemic dose does not exceed the MTD (if established) or 80 µg total dose (20 µg injected in 4 lesions). This analysis is designed to be exploratory and will evaluate safety, clinical outcome and exploratory biomarkers to guide further clinical development. Clinical efficacy including ORR and DOR will be evaluated in relapsed or refractory FL patients who received  $\geq 3$  prior systemic therapies.

For this analysis, 22 efficacy evaluable patients will be required. Efficacy evaluable patients are patients who received at least 3 doses of G100 at 20 µg/lesion and at least 1 dose of pembrolizumab, had at least one post baseline tumor assessment, and had no major protocol deviations that impact the efficacy of the study treatment or the assessment of response. Patients who received G100 20µg/lesion during Dose Escalation in Part 4 may be included in clinical response analysis. With a target ORR of 40%, if  $\leq 5$  responders are observed among 22 evaluable patients, we will conclude futility with 7.2% error rate. The Sponsor will use this analysis to decide whether to continue further development of this regimen. Early acceptance of treatment at the end of the 22 evaluable patients is not permitted. If the true ORR for this

group is 20% and 20% ORR is considered not clinically meaningful, the probability of observing  $\leq 5/22$  responders and stopping the study is 73.3%.

In Part 5, G100 Plus rituximab, after Dose Escalation has been completed, patients will be treated with intratumoral G100 at the recommended dose level in combination with rituximab. The purpose of this Patient Expansion group will be to explore the safety and clinical outcome of patients treated at a biologically active and safe G100 dose level administered into single tumor lesion in combination with rituximab. This analysis is designed to be exploratory and will evaluate safety, clinical outcome and exploratory biomarkers.

An exploratory analysis will be performed on 20 efficacy evaluable relapsed or refractory FL patients and will include analyses of the frequency and duration of CRs. Efficacy evaluable patients are patients who received at least 3 injections of G100 at the recommended dose and 3 doses of rituximab, had at least one post baseline tumor assessment, and had no major protocol deviations that impact the efficacy of the study treatment or the assessment of response. Five or more CRs in 20 patients treated with G100 plus rituximab will signal an improvement of CR rate over 10%. For reference, the probability of observing  $\leq 4$  CRs in 20 patients is 5.1% if the true CR rate is 40% (the targeted CR rate). Patients who received G100 at the recommended dose during Dose Escalation in Part 5 may be included in clinical response analysis. With 20 efficacy evaluable patients, and a historical CR rate of 10%, assuming a true CR rate of 32% in the G100 plus rituximab, this subgroup analysis has 82% power to detect a signal of an improvement in CR from 10% at a 1-sided alpha of 0.05.

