In Part 5, G100 Plus Rituximab, treatment may begin after enrollment into Part 3 has been completed (as determined by Sponsor), and an acceptable safety profile has been determined by the Sponsor in consultation with the DMC. In Part 5, patients will be enrolled to receive IT G100 and standard induction rituximab without radiation therapy. During dose escalation, sequential cohorts of 3-6 patients will be treated with intratumoral G100 at 20, 40, 60 or 80 μ g/dose into a single tumor mass. Once the MTD/maximum safe dose has been established, all safety, clinical and biomarker data will be reviewed and a recommended dose for further exploration will be made. The Patient Expansion would then begin and would treat patients with G100 at the recommended dose in a single lesion in combination with rituximab. Overall, 20 efficacy evaluable patients as defined in the Statistical Section will be enrolled.

Potential Dose Modification During Dose Escalation:

During Part 4 and based on the continuous review of safety events, if the dose of 20 μ g/lesion G100 is subsequently determined to have an increased safety risk, the DMC may recommend and the Sponsor may choose to reduce the dose of G100 to 10 μ g and potentially to re-examine escalation with this lower dose/lesion regimen or they may recommend stopping the G100 treatment.

G100 is a local therapy with systemic immune responses. Therefore, the safety profile may differ from that of systemically administered agents. In order to further investigate this, if 2 or more DLTs are observed in the initial cohort at 20 μ g of G100, the Sponsor, in agreement with the independent DMC may choose to examine a new cohort of patients to better understand whether or not the DLTs associated with the injection of a single lesion might be abrogated by decreasing the dose and administering the lower single lesion dose of 10 μ g into multiple

lesions. Intratumoral G100 10 µg in a single lesion in combination with pembrolizumab was established to be well-tolerated in Part 2 of this study. Thus, this new cohort would examine the safety of G100 10 µg administered into 2 injectable lesions and would use the same 3+3 design described above. Based on a review of the safety profile of this new cohort and in agreement with the independent DMC, further dose escalation cohorts may be investigated using this lower dose of 10 µg/lesion and a similar dose escalation schema as described above where up to 4 lesions may be potentially treated.

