Patient enrollment will be monitored. It is planned that 22 efficacy evaluable patients will be treated with intratumoral G100 and IV pembrolizumab in Part 4 in order to provide sufficient data for evaluation of efficacy (see Statistical Section). Patients who received G100 20 μ g/lesion during Dose Escalation in Part 4 may be included in the clinical response analysis.

Part 5, G100 Plus Rituximab: Studies have demonstrated the potential for additive or synergistic effects of the combination of G100 and rituximab. G100 has been shown to increase the number of inflammatory and activated immune cells within the tumor microenvironment, including T cells, NK cells, macrophage and dendritic cells. Rituximab can potentially increase the loading/pulsing of dendritic cells with tumor antigen, leading to more effective antigen presentation of rare tumor antigens. Rituximab and other similar antibodies that bind to tumor cells and debris have been previously shown to facilitate the uptake and processing of tumor antigens by dendritic cells through opsonization/phagocytosis. In addition, a known mechanism of action of rituximab is through antibody dependent cellular toxicity (ADCC). In preclinical work, the combination of G100 with rituximab demonstrated enhanced ADCC. Therefore, G100 in combination with rituximab can increase the amount of tumor antigen processed by dendritic cells potentially leading to greater T cell stimulation/activity; in addition, the combination could enhance tumor cytotoxicity by activating and increasing the number of ADCC effector cells.

In this study, a Dose Escalation will be performed first followed by Patient Expansion. During Dose Escalation 12-24 patients and during Patient Expansion 20 efficacy evaluable patients as defined in the Statistical Section will be enrolled. Patient enrollment will be monitored. Patients who received G100 during Dose Escalation in Part 5 may be included in clinical response analysis.

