7.0 SELECTION OF PATIENTS

This study plans to enroll patients with follicular NHL and other indolent lymphomas. In Part 1, Dose Escalation, up to 12 evaluable patients may be enrolled. In Part 2, for the Patient Expansion With or Without Pembrolizumab group, up to 24 additional patients and for the optional Large Tumor Group up to 4 evaluable patients will be enrolled. In Part 3, G100 Expansion of 20 µg Dose Group, up to 25 patients may be enrolled. In Part 4, Sequential G100 at 20 µg/lesion Into Single Or Multiple Tumor Masses Plus Pembrolizumab Group, 22 efficacy

evaluable patients will be enrolled. In Part 5, G100 Plus Rituximab, 12-24 patients will be enrolled during Dose Escalation and 20 efficacy evaluable patients, during Patient Expansion.

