40 $\mu$ g dose level	20 $\mu$ g in up to 2 lesions
60 $\mu$ g dose level	20 $\mu$ g in up to 3 lesions
80 $\mu$ g dose level	20 $\mu$ g in up to 4 lesions

Patient enrollment will be monitored. It is planned that 22 efficacy evaluable patients will be treated with intratumoral G100 and IV pembrolizumab in Part 4 in order to determine if it's unlikely to reach the target ORR of 40%. Patients who received G100 20 $\mu$ g/lesion during Dose Escalation in Part 4 may be included in the clinical response analysis.

*Part 5, G100 Plus Rituximab:* Studies have demonstrated the potential for additive or synergistic effects of the combination of G100 and rituximab. G100 has been shown to increase the number of inflammatory and activated immune cells within the tumor microenvironment, including T cells, NK cells, macrophage and dendritic cells. Rituximab can potentially increase the loading/pulsing of dendritic cells with tumor antigen, leading to more effective antigen presentation of rare tumor antigens. Rituximab and other similar antibodies that bind to tumor cells and debris have been previously shown to facilitate the uptake and processing of tumor antigens by dendritic cells through opsonization/phagocytosis. In addition, a known mechanism of action of rituximab is through antibody dependent cellular cytotoxicity (ADCC). In preclinical work, the combination of G100 with rituximab demonstrated enhanced ADCC. Therefore, G100 in combination with rituximab can increase the amount of tumor antigen processed by dendritic cells potentially leading to greater T cell stimulation/activity; in addition, the combination could enhance tumor cytotoxicity by activating and increasing the number of ADCC effector cells.

In this study, a Dose Escalation will be performed first followed by Patient Expansion ([Figure 6](#), [Figure 7](#)). During Dose Escalation 12-24 patients and during Patient Expansion 20 efficacy evaluable patients as defined in the Statistical Section of the protocol will be enrolled. Patient enrollment will be monitored. Patients who received G100 during Dose Escalation in Part 5 may be included in clinical response analysis.

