Following completion of the dose escalation stage of the trial, the MTD will be defined as the highest dose reached in which less than one third of the patients in the cohort experienced a DLT. If no DLTs are experienced in the first 3 patients enrolled at highest dose of 80µg, the 80µg dose per lesion will be determined to be the “maximum safe dose” examined in this study and dose escalation will be considered complete. An additional 3 patients may then be enrolled for a total of 6 patients at that dose level and safety stopping rules will be followed. If after the Sponsor and DMC review all safety data it is determined that there are no safety issues requiring the separation of the first dose of rituximab and G100, the regimen may be modified to administer both on Day 0 during Patient Expansion.

*Part 5, Patient Expansion:* Once the MTD/maximum safe dose has been established, all safety, clinical and biomarker data will be reviewed and a recommended dose for further exploration will be made. The Patient Expansion would then begin and would enroll patients to receive G100 IT at the recommended dose into a single tumor mass in combination with rituximab. ORR in patients enrolled on Part 5 Patient

Expansion will be analyzed. An exploratory analysis will also be performed in those who are considered TLR4high.

Patients will be enrolled with the intent of obtaining data from at least 20 efficacy evaluable patients. Patients who received G100 at the recommended dose during Dose Escalation in Part 5 may be included in clinical response analysis.

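### SAP 4.2, read literally, drops every Part 4 and Part 5 patient from the Safety Population; separately, the Part 5 rule of 5 CRs in 20 does not say in advance which 20 patients it covers

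*SAP*

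**What the plan says.** **Safety Population.** SAP 4.2 requires at least one G100 injection and makes prior local radiation part of the condition. SAP 5.7 bases all safety evaluation on this set, and SAP 5.6 uses it for a supportive efficacy analysis. SAP 3.1 omits radiation in Parts 4 and 5, and Protocol 8.3 says the same.

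**Part 5 rule.** SAP 3.4 and Protocol 14.2 set one numeric efficacy rule: "Five or more CRs in 20 patients treated with G100 plus rituximab will signal an improvement of CR rate over 10" percent. They quote 82% power at a true CR rate of 32%, at 1-sided alpha 0.05. For this rule an evaluable patient needs at least 3 G100 injections at the recommended dose, 3 rituximab doses, a post-baseline tumour assessment and no major deviation affecting efficacy. The same paragraph adds: "Patients who received G100 at the recommended dose during Dose Escalation in Part 5 may be included in clinical response analysis".

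**Which 20.** The descriptions differ:
- Protocol 6.1: "During Dose Escalation 12-24 patients and during Patient Expansion 20 efficacy evaluable patients". Protocol 7.0: "enrolled during Dose Escalation and 20 efficacy evaluable patients, during Patient Expansion". SAP 3.1: "during Patient Expansion 20 efficacy evaluable patients as defined in the Statistical Section of the protocol will be enrolled".
- SAP 3.1, Part 5 Patient Expansion: "Patients will be enrolled with the intent of obtaining data from at least 20 efficacy evaluable patients".
- Protocol 4.7, and the Synopsis under Safety Monitoring: "Overall, 20 efficacy evaluable patients as defined in the Statistical Section will be enrolled".

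SAP 3.4 limits the optional patients to the recommended dose. Protocol 4.1, Protocol 6.1 and the general Part 5 text of SAP 3.1 allow escalation patients with no dose limit.

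**Label.** SAP 4.3 gives the name Efficacy Evaluable to a wider set, with one G100 injection enough, than the SAP 3.4 definitions for the Part 4 and Part 5 rules.

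**The concern.** Safety is in the primary objective of both Parts 4 and 5. A programmer who follows SAP 4.2 to the letter would produce safety tables with no patients from either part.

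For Part 5, preliminary efficacy is also in the primary objective, and the 5-of-20 rule is the only numeric efficacy criterion. SAP 5.6.2, where response is analysed, has no CR rule that would settle the set. The trial is open label, and efficacy data are among those reviewed when the Expansion dose is chosen. The responses of the optional escalation patients can therefore be known when someone decides whether to count them. The quoted alpha does not cover that choice.

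**Working it through.** **1. Safety Population: the passages side by side**

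| Source | Condition for the safety set | Part 4 and 5 patients |
|---|---|---|
| SAP 4.2 | G100 injection following local radiation | excluded |
| Protocol Synopsis (Safety Monitoring) and 4.7 | one or more G100 injections | included |
| Protocol 14.3.1 | one injection or a study-related procedure | included |
| SAP 5.7.1 | reports radiation exposure for Parts 1 to 3 only | implies other parts are in the set |

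No reading of the words in SAP 4.2 keeps a patient who had no radiation.

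**2. Part 5 rule**

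Inputs: n = 20, cut 5, null rate 0.10 and alternative 0.32 (SAP 3.4). Escalation cohort size m = 3 or 6: SAP 3.1 expands a cohort from 3 to 6 after one DLT, and says of the top dose, "An additional 3 patients may then be enrolled for a total of 6 patients at that dose level".

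*The plan's own figures.* Let X be Binomial(20, p).
- P(X ≥ 5 | 0.10) = 1 − (0.12158 + 0.27017 + 0.28518 + 0.19012 + 0.08978) = 1 − 0.95683 = 0.0432.
- P(X ≥ 5 | 0.32) = 0.8173, which is the stated 82%.
- P(X ≤ 4 | 0.40) = 0.0510, which is the stated 5.1%.

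All reproduce. They hold for 20 patients fixed before responses are known.

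*Counted within the 20 by a prior rule, dose not chosen on CRs.* The total is still Binomial(20, 0.10), so alpha stays at 4.3%.

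*Choice after the fact between two sets of 20.* One set is 20 Expansion patients. The other is m escalation patients plus the first 20 − m Expansion patients. Let A ~ Bin(20 − m, 0.10) be the shared Expansion patients, B ~ Bin(m, 0.10) the last m Expansion patients, and E ~ Bin(m, 0.10) the escalation patients. The rule can be met if A + max(B, E) ≥ 5. For m = 3:

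| max(B, E) = j | probability | P(A ≥ 5 − j), A ~ Bin(17, 0.10) | product |
|---|---|---|---|
| 0 | 0.5314 | 0.0221 | 0.0118 |
| 1 | 0.4133 | 0.0826 | 0.0342 |
| 2 | 0.0532 | 0.2382 | 0.0127 |
| 3 | 0.0020 | 0.5182 | 0.0010 |

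Unrounded, the sum is 0.0596, or 6.0%. The same calculation with m = 6 gives 0.0679, or 6.8%. Neither figure assumes that the dose was selected on response.

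*The mildest use.* Claim a signal if either 5 of the 20 Expansion patients, or 6 of the pooled 23, have a CR. The addition to 0.0432 is P(X = 4)·P(E ≥ 2) + P(X = 3)·P(E = 3) = 0.08978 × 0.028 + 0.19012 × 0.001 = 0.0027. Alpha is 0.0459, or 4.6%, still under 0.05. With 6 escalation patients (6 of 26) it is 5.7%.

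**The case against.** **The analysis is exploratory.** SAP 3.4 says so, Protocol 14.1 says it of all analyses, and SAP 8 reports nominal p-values outside the nanostring work. The Part 5 rule only signals an improvement; unlike the Part 4 rule, no development decision is tied to it. This stands, and it is why the second point is minor. It does not excuse quoting an alpha that the rule as worded does not secure.

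**Pooling is not a fault in itself.** Correct: within a prespecified 20, with the dose not chosen on CRs, alpha is 4.3%. The gap is the undefined choice.

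**It may be moot.** SAP 9 records sponsor termination, and the SAP specifies no rituximab exposure summary and no table of rituximab-related events. The documents do not state Part 5 enrolment. If nobody was treated in Part 5, the second point has no practical effect. But SAP 9 withdraws only the Lugano assessment and the Part 4 independent radiology review, not the Part 5 rule.

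**The radiation clause is plainly a leftover.** Probably so, since the protocol's intent is clear. The text still needs correcting.

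**Stronger readings that the documents do not support.** A reader might infer an alpha of 7.3% or 11.2% from adding 3 or 6 escalation patients on top of 20. That needs the cut of 5 kept at n = 23 or 26, and the plan applies 5 only to 20. A reader might also infer 8.3% (m = 3) or 10.3% (m = 6), by counting within the 20 the best of four escalation cohorts. That needs the dose to be chosen purely on CRs. SAP 3.1 describes a joint review of safety, efficacy and biomarkers and names no CR criterion. At a 10% CR rate a cohort of 3 has no CR with probability 0.9³ = 0.73, so CR counts would often say little.

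**Conclusion.** The Safety Population definition is wrong as written: it excludes all of Parts 4 and 5 and conflicts with three places in the protocol. A reader might take the exclusion as deliberate, but the protocol text and SAP 5.7.1 point the other way.

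The Part 5 point holds and is minor. The plan's arithmetic is correct, but its alpha of 4.3% and power of 81.7% belong to a set of 20 that the plan does not fix. Free choice between two sets of 20 gives 6.0% to 6.8%, assuming independent patients, a true CR rate of 10%, and one recommended-dose cohort of 3 or 6. Not every use exceeds 0.05; the mildest gives 4.6%. What is at stake is the quoted error rate of an exploratory signal.

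**What to change.** 1. **SAP 4.2.** Delete the radiation condition, or limit it to Parts 1 to 3. No cost.
2. **SAP 3.4 and Protocol 14.2.** Before Part 5 response data are reviewed, state: the 5-CR rule is applied to the first 20 Expansion patients, in enrolment order, who meet the SAP 3.4 definition; recommended-dose escalation patients are reported separately as supportive.
3. **Align** the Protocol Synopsis (Trial Design and Safety Monitoring), Protocol 4.1, 4.7, 6.1 and 7.0, and the Part 5 text of SAP 3.1, on both the meaning of 20 and the recommended-dose limit.
4. **SAP 4.3.** Rename the set, or say that it does not replace the SAP 3.4 definitions for the Part 4 and Part 5 rules.

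The cost is wording, and escalation responses no longer inform the rule. If 20 in Expansion was the intent, no patients are added. If 20 overall was the intent, counting recommended-dose escalation patients within the 20 is acceptable under a rule written in advance, with a note that alpha is 4.3% only if the dose was not chosen on CRs.
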